10.2 Primary Efficacy Sensitivity Analyses

The analysis outlined in section 10.1 will be repeated using the PP population. The following additional sensitivity analyses will be performed for the ITT population, using placebo and selected dose of Flebogamma[®] 5% DIF 2MWD data from Stages 1 and 2 combined.

- 1. An MMRM using the same model used in the primary analysis. Least squares (LS) means and 95% CIs will be presented and plotted by visit and treatment group.
- 2. An analysis of covariance (ANCOVA) will be performed with change in 2MWD from baseline to 52 Week as the dependent variable, treatment and main part of the body most significantly affected (lower/upper extremities) by PPS as the fixed effects, and baseline 2MWD measure as covariate. Data missing at 52 Week will be imputed using the Last (post-baseline) 2MWD Observation Carried Forward [LOCF]. LS means and 95% CIs for treatment effect and treatment comparison at week 52 will be provided

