4.1 Primary and secondary endpoints

Primary efficacy endpoint will be:

Physical performance (2MWD) from baseline to the end of the treatment period (at End of Treatment Visit -Week 52).

Secondary efficacy endpoints will be:

- Pain (VAS of pain) from baseline to the end of the treatment period.
- HROoL (SF-36 PCS) from baseline to the end of the treatment period.
- Endurance (6MWD) from baseline to the end of the treatment period.

Safety endpoints will include adverse events (AEs), vital signs during infusions, physical assessments and blood tests for clinical safety.

Description of the design of the trial to be conducted and a schematic 4.2 diagram of trial design, procedures and stages

This is a phase II/III multi-centre, prospective, randomized, placebo-controlled, double-blind, parallel-group clinical trial with an adaptive design (flexible group sequential design with adaptive dose selection) in subjects with PPS.

This study will consist of 2 stages (Figure 1). The first stage (Stage 1) is for dose selection (Figure 2), and the second stage (Stage 2) is to establish the superiority (efficacy confirmation) of Flebogamma[®] 5% DIF (Figure 3) in the change in physical performance (2MWD) as compared to the placebo and for overall safety analysis, by combining the data from both stages, in PPS subjects.

Stage 1 will be a 3-arm evaluation of 2 active dose levels of Flebogamma[®] 5% DIF (IVIG 1 g/kg and 2 g/kg of body weight) and placebo randomized in a 1:1:1 ratio. At the end of Stage 1 (after at least 80% of the randomized subjects have finished the treatment period of Stage 1), a formal unblinded interim analysis will be performed by an independent Data Monitoring Committee (DMC). Based on a set of predefined criteria, 1 of the 2 active treatment groups will be selected

GRIFOLS IG1104 - A multicenter, pros

to continue to Stage 2 of the clinical trial. Subsequently, at Stage 2, a separate cohort of subjects will be randomized to receive either the selected dose from Stage 1 or placebo in a 1:1 ratio for efficacy confirmation and overall safety analysis. During both stages of the study, randomization will be stratified by the main part of the body most significantly affected by PPS, that is, lower extremities or upper extremities.

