10.1.2.2 Analysis of secondary efficacy endpoints

The data from Stage 1 and Stage 2 for the selected doses will be combined and the same approaches (e.g., MMRM or ANCOVA) used in the primary efficacy analyses will be applied to the analyses of the secondary efficacy endpoints. A fixed-sequence testing method will be employed to address the multiplicity issue for multiple secondary efficacy variables. The order in which the null hypotheses are tested is predetermined as below for all secondary efficacy variables:

Pain by a VAS for pain:
 Treatment effect in change in VAS score, for the pain in VAS score, for the pai

Treatment effect in change in VAS score, from baseline to the end of the treatment period, will be tested between the 2 treatment groups (test and placebo).

• HRQoL by the SF-36 PCS:

Treatment effect in change in SF-36 PCS score, from baseline to the end of the treatment period, will be tested between the 2 treatment groups (test and placebo).

• Endurance by the 6MWD:

Treatment effect in change in 6MWD, from baseline to the end of the treatment period, will be tested between the 2 treatment groups (test and placebo).

Each subsequent hypothesis is tested only if all previously tested null hypotheses have been rejected at a 2-sided significance level of 5%.

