10.1 Primary Efficacy Analyses

The primary efficacy variable is physical performance (2MWD) from baseline to the end of the treatment period (Week 52). The primary efficacy variable will be analyzed to compare each active treatment arm to placebo at Week 52 by using mixed-effect model repeated measures (MMRM) method separately for each stage.

The MMRM will include change from baseline in 2MWD as the dependent variable; treatment, protocol-specified visits, treatment-by-visit interaction, and main part of the body affected (lower extremity versus upper extremity) as the fixed effects; baseline 2MWD measure as a covariate; and measures within-subject at each visit as a repeated measure. covariance matrix will be assumed to be unstructured. If the procedure does not converge then a compound symmetric variance-covariance matrix will be used instead.

The least-squares means for each treatment arm and its differences along with p-values between Flebogamma® 5% DIF and placebo at Week 52 will be estimated separately for each stage. The sample SAS® code for MMRM model is below:

```
proc mixed data=pp method=ml;
   class Subject Treatment Visit Bodypart;
   model change = Baseline Bodypart Treatment Visit
                  Treatment*Visit / s;
   repeated Visit / type=un subject=Subject r;
   lsmeans Treatment*Visit / pdiff cl;
run;
```

The overall adjusted p-value for the selected dose of Flebogamma® 5% DIF vs placebo at Week 52 will be calculated from the p-values of both Stage 1 and Stage 2 by the method proposed by Posch & Bauer (2005) in order to control the overall type I error rate for testing the equal means between the selected dose and placebo:

```
H_0: \mu_{flebogamma} - \mu_{placebo} = 0 (or equivalently H_0: \mu_{flebogamma} = \mu_{placebo})
```

versus

```
H_A: \mu_{flebogamma} - \mu_{placebo} \neq 0 \; (\mu_{flebogamma} - \mu_{placebo} > 0 \; or \; \mu_{flebogamma} - \mu_{placebo} < 0)
```

where $\mu_{flebogamma}$ and $\mu_{placebo}$ are the mean change of 2MWD for the selected Flebogamma[®] 5% DIF dose group and placebo respectively. The superiority will be deemed to have been demonstrated if the two-sided overall adjusted p-value is less than or equal to 0.05 and $\mu_{flebogamma} - \mu_{placebo} > 0.$

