10.3 Secondary Efficacy Analyses

The MMRM and ANCOVA analyses using combined data from Stages 1 and 2, described in section 10.2, will be performed and LS means will be plotted by visit and treatment group for each of the secondary efficacy variables listed in section 4.1.2.

A fixed-sequence testing method will be employed to address the multiplicity issue for multiple secondary efficacy variables. The order in which the null hypotheses will be tested is predetermined as follows:

- 1. Pain (VAS of pain) from baseline to the end of the treatment period (Week 52).
- 2. Health-related quality of life (SF-36 PCS) from baseline to the end of the treatment period (Week 52).
- 3. Endurance (6MWD) from baseline to the end of the treatment period (Week 52).

The outcome of each subsequent hypothesis tested will be evaluated only if all previously tested null hypotheses have been rejected at a two-sided significance level of 5%.

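### The pooled Stage 1 + Stage 2 MMRM and ANCOVA omit stage, which costs some precision if the separately randomised stages differ in mean change

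*SAP*

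**What the plan says.** - **Primary model (SAP 10.1).** Week 52 is analysed "by using mixed-effect model repeated measures (MMRM) method separately for each stage". The model has "treatment, protocol-specified visits, treatment-by-visit interaction, and main part of the body affected (lower extremity versus upper extremity) as the fixed effects", with baseline 2MWD as covariate. The sample code has "class Subject Treatment Visit Bodypart" and no stage variable.
- **Pooled models (SAP 10.2).** Placebo and selected-dose data from both stages are combined and analysed with "An MMRM using the same model used in the primary analysis". The accompanying ANCOVA has "treatment and main part of the body most significantly affected (lower/upper extremities) by PPS as the fixed effects, and baseline 2MWD measure as covariate".
- **Secondary endpoints (SAP 10.3).** "The MMRM and ANCOVA analyses using combined data from Stages 1 and 2, described in section 10.2, will be performed" for pain, SF-36 PCS and 6MWD, tested in fixed sequence at two-sided 5%. Protocol 10.1.2.2 agrees: "The data from Stage 1 and Stage 2 for the selected doses will be combined and the same approaches" as for the primary endpoint are to be used, with no stage term named.
- **Exploratory endpoints (SAP 10.4).** A pooled MMRM is used, again with no stage term.
- **Design.** Protocol 4.2 describes Stage 2 as "a separate cohort of subjects" randomised 1:1. Stage 1 is randomised 1:1:1. Randomisation is stratified by body part in both stages.

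Outside the per-stage primary analysis, the SAP uses stage only for presenting results (Section 5 and the descriptive summaries). It enters no pooled model.

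**The concern.** Leaving stage out is right for a model fitted inside one stage. Once the stages are combined, the same model treats two consecutive cohorts, randomised separately and recruited at different times, as one sample. The plan adjusts for body part, the stratification factor within each stage, but not for the cohort itself. The primary test respects stage by combining stage-wise p-values; the pooled tests do not.

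If mean change differs between the cohorts, that difference goes into the residual. Standard errors and confidence intervals for the secondary and exploratory endpoints, and for the pooled 2MWD sensitivity analyses, are then too wide. The secondary tests are in fixed sequence, so a loss on pain, which is tested first, stops the sequence before PCS and 6MWD.

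**Working it through.** **Inputs.** Difference 6 m, SD of change 11 m, 33 evaluable per arm per stage, 20% dropout (Protocol 10.2, SAP 5.3); two-sided alpha 0.05 (Protocol 10.3). The stage shift is an assumption, because the documents give none; 0.25 to 1 SD is shown.

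**The plan's own figure.** 33/0.80 = 41.25, rounded up to 42 per arm; 3 × 42 = 126 and 2 × 42 = 84. Both match. The plan states no power, so the baseline has to be computed.

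**Power with no stage shift, or with stage in the model.** Pooled, there are 66 per arm. SE = 11 × √(2/66) = 1.915; 6/1.915 − 1.960 = 1.173; power = Φ(1.173) = 88.0%.

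**Effect of omitting stage.** With equal stages and balanced arms, a shift d between stages adds d²/4 to the residual variance:

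pooled SD = √(11² + d²/4).

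For d = 5.5 m: √(121 + 7.56) = 11.34; SE = 11.34 × √(2/66) = 1.974; 6/1.974 − 1.960 = 1.080; power = 86.0%. The interval widens by 11.34/11 − 1 = 3.1%. Because the arms are balanced within stage, the shift cancels from the treatment difference and only its estimated standard error grows. Test size is therefore 2 × [1 − Φ(1.960 × 11.34/11)] = 0.043.

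The formula was checked by simulating linear models with and without a stage term (40,000 replicates per scenario):

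| Assumed shift | Pooled SD | Interval width | Power without stage, formula | Power without stage, simulated | Power with stage, simulated | Size without stage, formula / simulated |
|---|---|---|---|---|---|---|
| 0.25 SD (2.75 m) | 11.09 | +0.8% | 87.5% | 87.6% | 87.9% | 0.048 / 0.049 |
| 0.5 SD (5.5 m) | 11.34 | +3.1% | 86.0% | 86.0% | 87.4% | 0.043 / 0.043 |
| 1 SD (11 m) | 12.30 | +11.8% | 80.0% | about 82% | 87.5% | 0.028 / 0.029 |

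The power formula is somewhat pessimistic at the largest shift because it counts the cancelled shift as sampling noise. The mean treatment estimate was about 6 m with either model, so there is no bias. Unequal stage sizes with balanced arms (26 per arm, then 45 per arm, as under-running in Stage 1 could produce) also gave no bias, with size 0.044 at 0.5 SD.

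**Scale.** The documents give no planning SD of change for VAS pain, PCS or 6MWD. The width ratio is √(1 + k²/4) for a shift of k SD, so the relative effect carries over to those endpoints in SD units; the metres do not.

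**Degrees of freedom.** The treatment period has four post-baseline visits (Weeks 12, 24, 36, 52). Stage takes 1 and stage-by-visit 3, so 4. With Weeks 64 and 76 it is 1 + 5 = 6.

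**The case against.** The strongest reply is that nothing goes wrong under the plan as designed. Allocation between selected dose and placebo is 1:1 in both stages, the estimate is unbiased, the test errs on the safe side, and the primary test is untouched. Large shifts are also hard to credit. The cited natural decline of 0.9% a year on 120 m is about 1.1 m, which adds only 1.1²/4/121, or about 0.2%, to the variance. A shift of 0.5 SD (5.5 m) is nearly the whole 6 m effect sought. All of this stands and keeps the point small. It does not explain why a model built for one stage should be reused unchanged on two.

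A reader might go further and infer confounding: that missing data, for instance after early termination, biases the pooled comparison. This needs the arms to be unbalanced differently in the two stages. As an illustration, 29 active and 38 placebo analysed in Stage 1, reversed in Stage 2, gives a bias of (38 − 29)/67 = 0.134 of the shift, or about 0.4, 0.7 and 1.5 m at 0.25, 0.5 and 1 SD. Simulated size is then 0.052, 0.061 and 0.078. The documents show no such pattern. SAP 2 describes a business decision with no safety concern, after which enrolled subjects could complete blinded treatment.

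A reader might also infer that the pandemic measures affected the stages differently. Their content is in Annex 18, which is not in the available text, so this cannot be supported.

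**Conclusion.** The omission is real in both pooled models and affects the secondary tests, the exploratory MMRM and the pooled 2MWD sensitivity analyses. It is a minor precision and pre-specification gap, not a validity problem. By the formula the power loss is about 0.5, 2 and 8 points at assumed shifts of 0.25, 0.5 and 1 SD, and by simulation it is no larger (about 5 points at 1 SD). The test is conservative throughout. These figures assume balanced arms, equal stages and the 2MWD planning inputs.

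The point applies only if Stage 2 enrolled subjects. SAP 2 and 12.1 report early termination without saying so; if it enrolled none, there is nothing to pool and the omission has no effect. Nor should a stage term be read as a remedy for selecting the dose on Stage 1 data: that is a separate matter, and adding stage does not address it.

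**What to change.** In SAP 10.2, define the pooled models explicitly instead of by reference to the per-stage model: add stage and stage-by-visit as fixed effects to the MMRM, and stage to the ANCOVA. Carry this into 10.3 (both models) and 10.4 (MMRM), before unblinding so that the model is not chosen after the data are seen. A descriptive treatment-by-stage check can be reported alongside.

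The cost is a few lines of text and code, one degree of freedom in the ANCOVA, and about 4 in the MMRM (6 if Weeks 64 and 76 are modelled; fewer for exploratory endpoints measured at fewer visits). State in the SAP whether Stage 2 enrolled anyone; if it did not, say that the pooled analyses will not be performed.

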10.3 Secondary Efficacy Analyses

The MMRM and ANCOVA analyses using combined data from Stages 1 and 2, described in section 10.2, will be performed and LS means will be plotted by visit and treatment group for each of the secondary efficacy variables listed in section 4.1.2.

A fixed-sequence testing method will be employed to address the multiplicity issue for multiple secondary efficacy variables. The order in which the null hypotheses will be tested is predetermined as follows:

- 1. Pain (VAS of pain) from baseline to the end of the treatment period (Week 52).
- 2. Health-related quality of life (SF-36 PCS) from baseline to the end of the treatment period (Week 52).
- 3. Endurance (6MWD) from baseline to the end of the treatment period (Week 52).

The outcome of each subsequent hypothesis tested will be evaluated only if all previously tested null hypotheses have been rejected at a two-sided significance level of 5%.

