For sensitivity analysis of combined data in 2MWD from Stage 1 and Stage 2 for the selected dose group of IVIG versus placebo, an analysis of covariance (ANCOVA) method with change from baseline in 2MWD as the dependent variable, treatment and main part of the body most significantly affected (lower/upper extremities) by PPS as the fixed effects, and baseline 2MWD measure as covariate. Missing data will be imputed using a last-observation carried forward approach for post-baseline 2MWD measurement.

The analyses performed on ITT will be repeated for the PP population.

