10 EFFICACY ANALYSES

Analysis will be performed for each individual stage for the primary endpoint (2MWD) only and the significance of the treatment effect at each stage will be combined to provide an overall assessment of treatment efficacy. For secondary and exploratory endpoints, analyses will be performed over the two stages combined, using the placebo and selected dose of Flebogamma[®] 5% DIF treatment groups only.

Efficacy analyses will be performed on the ITT population. The ITT analyses will be performed according to the treatment randomized, not the actual treatment received. The primary efficacy analyses will also be performed on the PP population.

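### The secondary fixed sequence starts at pain and is not conditional on the adjusted 2MWD test, so as listed pain is tested at two-sided 5% even after a failed primary

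*SAP*

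**What the plan says.** SAP 10.3 sets the multiplicity rule: "A fixed-sequence testing method will be employed to address the multiplicity issue for multiple secondary efficacy variables". It numbers three steps (pain, SF-36 PCS, 6MWD) and says that the outcome of each later hypothesis "will be evaluated only if all previously tested null hypotheses have been rejected at a two-sided significance level of 5" percent. Protocol 10.1.2.2 has the same rule and the same three endpoints: "The order in which the null hypotheses are tested is predetermined as below for all secondary efficacy variables".

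The primary has its own test at the full level. SAP 10.1: "The superiority will be deemed to have been demonstrated if the two-sided overall adjusted p-value is less than or equal to 0.05", together with a difference above zero. SAP section 5 sets two-sided 0.05 as the default for all inference.

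The secondary tests pool the stages. SAP section 10: "For secondary and exploratory endpoints, analyses will be performed over the two stages combined, using the placebo and selected dose". The Protocol synopsis and SAP section 10 mention no link from the primary result to the secondary tests, and we found none elsewhere in either document.

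**The concern.** A fixed sequence protects the error rate across the hypotheses that it contains. Here it contains only the three secondaries. The rejection condition applies to each later hypothesis in the list, and pain is first, so nothing written conditions pain on 2MWD. The plan therefore has two procedures side by side, each at a full 5%: the adjusted 2MWD test, and the sequence that opens at pain.

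The case that matters is a failed 2MWD test with a pain p-value below 0.05. The pain result would have passed the pre-specified multiplicity procedure, and the plan does not say how it is then to be regarded. That should not be left to interpretation once results are known.

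**Working it through.** **1. The plan's own figure.** Three ordered tests, each at two-sided 0.05, stopping at the first non-rejection, have familywise error of at most 0.05 within the three secondaries. The first step has level 0.05. So the stated 5% reproduces for the secondary family taken alone (treating the pooled tests at face value). That level applies to pain whatever happened on 2MWD.

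**2. Primary plus pain, simple bound.** Two independent two-sided 5% tests with no link: 1 - 0.95 x 0.95 = 0.0975, or 9.75%. The Bonferroni bound is 0.05 + 0.05 = 10%. With 2MWD as a precondition it is at most 5%. Positive correlation between the two test statistics lowers the unlinked figure: 9.5% at 0.3, 9.1% at 0.5, 8.3% at 0.7 and 7.0% at 0.9. The correlations are assumptions.

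**3. The planned two-stage design.** Inputs from the documents: SD 11 m and 33 evaluable per arm per stage (Protocol 10.2, SAP 5.3); the conditional-power dose rule (SAP 5.4); the Simes and inverse-normal adjusted p-value (SAP 10.1), taken at one-sided 0.025. Pain is tested on pooled data at two-sided 0.05. Assumptions: interim on 26 per arm (0.8 x 33 = 26.4), second-stage n of 33 in the conditional-power formula, bivariate normal endpoints, and correlation 0, 0.3, 0.6 or 0.9. SAP 5.4 describes s as a standard error although the formula uses it like an SD, so both were run: s = 11, and s = 11/sqrt(26) = 2.16. There were 1,000,000 simulated trials per null case (Monte Carlo standard error about 0.02 points).

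Global null, favourable direction only:

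| Quantity | s as SD | s as standard error |
|---|---|---|
| Primary alone | 2.3% | 2.0% |
| Pain favourable, primary failed | 2.1-2.7% | 1.9-2.7% |
| 2MWD or pain, as listed | 4.3-5.0% | 3.9-4.7% |
| 2MWD or pain, 2MWD as precondition | 2.3% | 2.0% |

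The third row is the sum of the first two, apart from rounding: for example 2.3 + 2.7 = 5.0 and 2.0 + 1.9 = 3.9. Repeating the runs moved the upper ends by about 0.1 point. Using 42 per arm with an interim on 33, closer to SAP 5.4, moved the null figures by at most about 0.2 point.

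**4. Cost of the precondition.** Suppose that pain has a true effect of 6/11 SD and both doses have 6 m on 2MWD. Pooled n is 33 + 33 = 66 per arm. Standardised effect: 6 / (11 x sqrt(2/66)) = 6 / 1.915 = 3.13. Power: Phi(3.13 - 1.96) = 88.0%. The simulation without the precondition gives the same 88.0% at correlation 0. Chance of a pain claim, as listed and then with the precondition (500,000 trials per case):

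| Correlation | s as SD | s as standard error |
|---|---|---|
| 0 | 88.0% to 78.7% | 88.0% to 77.0% |
| 0.3 | 88.9% to 80.8% | 88.3% to 78.7% |
| 0.6 | 90.1% to 83.4% | 88.7% to 81.0% |
| 0.9 | 91.5% to 87.2% | 89.4% to 84.7% |

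The smallest loss is 91.5 - 87.2 = 4.3 points and the largest 88.0 - 77.0 = 11.0 points.

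**5. What the precondition leaves.** The pooled secondaries carry no adjustment for dose selection. When 2MWD truly works, a null secondary tested after the precondition can reach 2.8% one-sided with both doses at 6 m, and 3.3% with 3 m and 6 m, at correlation 0.9 and with s as the SD (2.5% and 2.7% with s as the standard error).

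**The case against.** The strongest reply is that the condition on previously tested null hypotheses already covers 2MWD. The only null hypothesis written out in the efficacy sections is the 2MWD one, it comes just before the secondaries, and testing secondaries only after a successful primary is common practice. This reading is available but not compelled: the condition belongs to a list that is declared to be for the secondary variables and that opens with pain. A rule with two readings in the one case where they differ needs a sentence.

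A reader might infer that the sponsor plans to claim efficacy on pain after a failed primary. The documents do not support that. Superiority is defined only through 2MWD, and the secondary objectives (Protocol section 3, SAP 3.2.2) are to evaluate clinical effect. The error rates above therefore describe a false favourable test result; it becomes a false claim only if someone treats it as one.

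A reader might also infer that the primary test is inflated, or that pooling undermines the secondaries. Neither holds. The simulated primary error is 2.0-2.3% one-sided, and a stand-alone pooled secondary has a two-sided error of 4.5-5.0%.

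It is also fair to say that the figures describe the planned design. SAP sections 2 and 12.1 report early termination for business reasons, and the SAP does not say whether Stage 2 was enrolled. The gap in the rule does not depend on these figures.

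**Conclusion.** The concern holds as a gap in the stated testing order. As listed, pain is tested at two-sided 5% whatever the 2MWD result. Under the global null this roughly doubles the one-sided chance of a false favourable result on 2MWD or pain, from 2.0-2.3% to about 3.9-5.0%. For two independent two-sided tests the comparison is 9.75% against 5%. The simulated range rests on the planned sample sizes, normal endpoints and an assumed correlation of 0 to 0.9.

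It would go too far to say that the precondition brings every error down to that of the primary. That is true only under the global null; the small dose-selection effect in step 5 remains. Ordering within the three secondaries is sound and the primary is controlled, so this is a change that should be made rather than a flaw that invalidates the analysis.

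**What to change.** State the sequence in SAP 10.3 as: 2MWD (overall adjusted two-sided p-value at most 0.05 and difference above zero), then pain, SF-36 PCS and 6MWD, stopping at the first non-rejection. Record it in SAP section 12 as a clarification of Protocol 10.1.2.2, which carries the same list.

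The cost is wording only, with no new data. The statistical price is the 4 to 11 points in step 4, all in trials whose primary failed.

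Three notes, none of which carries the point:
- SAP 10.3 says "The MMRM and ANCOVA analyses using combined data from Stages 1 and 2, described in section 10.2, will be performed" without naming the analysis that moves the sequence on. The roles for the primary point to MMRM, since Protocol 10.1.2.1 and SAP 10.2 use LOCF ANCOVA as a sensitivity analysis; saying so would help.
- The pooled secondary estimates could be labelled as not adjusted for dose selection.
- If there are no Stage 2 data, the adjusted p-value lacks its Stage 2 component, and the SAP would need to say which primary test opens the sequence.
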